## **METHODS:**

**Trial Design:** This is a pragmatic open-label randomized-controlled trial. The patients were allocated to one of two arms: acupuncture with standard-of-care (SOC) and SOC only (Fig. 1). The study protocol was reviewed and approved by the Institutional Review Board in accordance with the Helsinki Declaration (0102-14-BNZ) and registered at [www.clinicaltrials.gov](http://www.clinicaltrials.gov) (NCT03398928). Trial methods and results were reported according to the Consolidated Standards of Reporting Trials (CONSORT) for non-pharmacologic interventions 2010 guidelines.

**Setting and participants:** Trial site investigators identified consecutive eligible patients admitted to internal medicine departments at Bnai-Zion Medical Center, a 450-bed, academic hospital located in Haifa, Israel. Physicians and nurses screened daily all hospitalized patients aged 65 years and more for delirium, regardless of baseline cognitive function, using the validated 4AT delirium screening tool. For patients found to have a positive 4AT screening result, investigators used the validated, four-feature-Confusion Assessment Method (CAM) tool to confirm the presence of subsyndromal delirium or delirium according to DSM-5 definition. Delirium was deemed to be present when both an acute and fluctuating course and inattention and either disorganized thinking or an impaired level of consciousness was identified, while subsyndromal delirium was defined as acute and fluctuating course criteria and any one of the three other criteria. Participants were considered eligible for the study if they met all study criteria. Informed consent was obtained from patients or their next-of-kin as detailed in a preceding manuscript. Patients were enrolled either at hospital admission (prevalent delirium) or during hospitalization (incident delirium). Patients with prevalent delirium were randomized within 48 hours of admission; patients with incident delirium were randomized within 48 hours of delirium occurrence. All patients were classified as having subsyndromal, hyperactive, hypoactive or mixed type delirium. Information was extracted from

patients, family and medical records to ensure that all study criteria are met before the patient or his/her next-of-kin was approached for consent.

*Inclusion criteria:*

- (1) Hospitalized to an inpatient internal medicine unit.
- (2) Age  $\geq$  65 years.
- (3) Diagnosed with delirium or subsyndromal delirium within the past 48 hours.

*Exclusion criteria:*

- (1) Having a contraindication to acupuncture (e.g., platelets  $\leq 20 \times 10^9/L$ ).
- (2) History of severe dementia (documented history and/or IQCODE score  $\geq 4$ ).
- (3) Acute neurological injury (stroke).
- (4) History of schizophrenia or a formal thought disorder.
- (5) Active acute alcohol or drug withdrawal.
- (6) History of end stage liver failure.
- (7) Communication barriers preventing delirium assessment.

**Interventions:** Enrolled patients were allocated to one of the following treatment groups:

1. Acupuncture with SOC (acupuncture group): up to 5 sessions of acupuncture in a 1-week period or until discharge, and SOC treatment for up to 1 week or until discharge.
2. SOC only (SOC or control group): up to 1 week or until discharge.

The development of the intervention protocol was inspired from the 2008 Medical Research Council guideline for developing complex interventions, as described in a previous manuscript. Acupuncture treatment was reported according to STRICTA guidelines in <http://www.stricta.info>.

**Acupuncture rationale:** The acupuncture was performed in a Traditional Chinese Medicine (TCM) style. Patients were categorized according to TCM syndromes of hyperactive delirium (Fire blazing and Phlegm fire); hypoactive delirium (Qi deficiency, Yang deficiency, Yang deficiency with Phlegm, and Qi obstructed), or mixed delirium (Blood and Qi deficiency, and

Yin deficiency). The TCM categorization was based on pulse diagnosis and clinical observation. Due to the difficulty of tongue examination and anamnesis in delirious patients, these elements were rarely used in the diagnostic process. Then, TCM-based acupuncture treatment was performed according to the delirium TCM syndrome category.

**Details of needling:** During the treatment, the acupuncturists used 75% alcohol pads to sterilize the skin around the acupoints. Subsequently, sterile disposable needles were inserted in the acupoints. An average of five Seirin FDA-approved needles of 5-cm length and 0.2-mm diameter were inserted. The puncture depth varied with anatomical location from 0.5 to 1 cm. Manual needle stimulation was performed and *de qi* sensation (e.g. dullness, sourness, heaviness, tingling sensation around the needle) was not sought.

**Treatment regimen:** The number of acupuncture treatments was set at up to five treatments in the one-week study period (treatments was not provided on weekends) or until the patient is delirium-free for 48 hours. Each session lasted 15-20 minutes.

**Other components of treatment:** Patients of acupuncture group also received SOC. Prior to the start of the study, a multicomponent protocol for delirium management was developed and implemented in internal medicine departments. This protocol was based on best literature evidence, current practice guidelines and the opinions of geriatric and psychiatric consultants, and included both pharmacological and non-pharmacologic interventions as published in a preceding manuscript. All clinicians working in the internal medicine departments were educated regarding the protocol and its use. This protocol was defined “SOC” for the study. Since the actual care of patients may differ according to clinical data and physician consideration, the use of psychotropic drugs (including antipsychotics) during hospitalization were documented and compared between the study arms. No other complementary medicine therapies other than acupuncture were added. Explanations were given to patients and their next-of-kin on potential benefits and side effects of acupuncture and treatment was administered only after they signed informed consent.

**Practitioner background:** The treatment was administered by seven acupuncturists with at least 5 years of clinical experience in a hospital setting.

**Control intervention:** In the control group, patients received SOC only.

**Outcomes:** All daily outcomes were collected daily for one week after randomization or until the patient was discharged from the hospital.

Primary outcome: Our primary endpoint was resolution of delirium during the 7 days of evaluation and was measured as time-to-first remission of delirium and number of delirium-free days, based on daily assessment of CAM scale.

Secondary outcomes:

1. *Delirium severity:* Comparison of the sum of long CAM-severity (CAM-S) score from day 2 (before treatment in the second day of the study) until day 7 (last day of evaluation). The CAM-S tool includes 10 delirium-related items, the first one being rated on a 0-1 scale and the nine followings in a 0-2 scale for a total score ranging from 0-19. The items include the four CAM items described earlier in addition to disorientation, memory impairment, perceptual disturbances, psychomotor agitation, psychomotor retardation and altered sleep-wake cycle. The sum of long CAM-S score has been shown to best reflect both 30-day and 90-day post-hospital outcomes in patients with delirium.
2. *Number of days an antipsychotic drug was administered:* as mentioned in the daily study investigator chart review.
3. *Pain:* based on twice daily Visual Analogue Scale (VAS) scores for communicating patients and FRAAC (Facial expression, Respiration, Activity, Audibility, Cry and consolability) scores for non-communicating patients. Both scales are rated on a 0-10 score and are comparable in terms of pain severity. They were routinely recorded twice daily by registered nurses.
4. *Sleep quality:* as assessed by the tenth CAM-S item.
5. *Delirium complications:* daily evaluation of falls, pulling-out intravenous or urinary catheters, new or increase in pressure ulcers grade.
6. *Length of hospital stay*
7. *Functional status at discharge:* based on Katz ADL at discharge as evaluated by study investigators.
8. *Safety and adverse events:* A checklist with acupuncture adverse events based on the AcupAE questionnaire was adapted to our study. All adverse events were recorded and monitored daily. Acupuncture-associated adverse events were discussed by the research team and the family of patients and addressed accordingly. Severe adverse events requiring patient exclusion

from the clinical trial included pneumothorax, massive bleeding, or infection in the acupoint area requiring systemic antibiotic treatment.

**Sample size calculation:** Since no previous study has evaluated an acupuncture-based intervention in older adults with delirium, a pilot study of 32 patients [acupuncture group (n=24); control group (n=8)] was designed to estimate accurately the sample size for our current study. In the pilot study, delirium-free days were  $3.2 \pm 1.6$  in the acupuncture group as compared with  $1.7 \pm 2.4$  in the control group. Taking into account a Type I error (alpha) of 0.05, a power of 0.80, pairwise comparison between our two study arms, and using G\*Power 3.1.9.4 software, we calculated a minimal sample size of 28 patients in each of the 2 study arms.

**Randomization:** Patients were randomized in two groups by convenience allocation according to acupuncturists' working days: patients with delirium diagnosed on Sunday, Monday, Wednesday or Thursday were assigned to the acupuncture arm, while patients with delirium diagnosed on Tuesday, Friday or Saturday were assigned to SOC arm. Blinding was clearly not feasible.

**Statistical methods:** Demographic and clinical data was analyzed at baseline to measure the balance among the study groups. Quantitative variables were described using mean and standard deviation or median with range (minimum and maximum) depending on their distribution. Qualitative variables were described using frequency and percentage distributions. Next, we showed that our variables distribute equally between the two groups. For comparing normally distributed variables between our study groups, we used the t-test for independent samples. For comparing variables that do not distribute normally between our study groups, we used the Mann-Whitney test. For comparing qualitative variables between our study groups, we used the independent Chi-square test and Fisher exact test. Time-to-first delirium remission was evaluated using the Kaplan-Meier product limit survival estimator with log-rank between-group comparison and Cox regression was performed for multivariate adjustment of potential confounders. Hazard ratio (HR) with confidence intervals (CI) was calculated for each independent variable and controlled for all other independent variables in the regression. Patients who died or were discharged before day 7 had all subsequent days counted as the last day of evaluation in terms of both CAM and CAM-S. Intention-to-treat (ITT) analysis was planned to provide more information on the effect of the intervention. We explored the variables for possible collinearities, interaction, and confounders. All comparisons were two-sided with

significance level set at  $p<0.05$ . Data analysis was performed using IBM SPSS version 22 statistics software.

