## Secondary endpoints:

*Delirium severity:* The long CAM-S sum from day 2 to day 7 of evaluation was significantly lower in the acupuncture group [11 (24%) with no delirium, 6 (13%) with low severity, 9 (20%) with moderate severity and 19 (42%) with high severity] as compared with the control group

[3 (11%) with no delirium, 0 with low severity, 1 (4%) with moderate severity and 24 (86%) with high severity], p=0.002, Fig. 3.

*Number of psychotropic drugs-free days:* The number of psychotropic drugs-free days in the 7 days of evaluation was similar in the two study groups [median: 7 (0-7) in acupuncture arm vs 7 (0-7) in SOC arm, p=0.253].

*Pain:* No difference in daily evaluation of pain intensity was found between the two study arms in the 7 days of evaluation.

*Sleep:* According to the tenth CAM-S item daily evaluation, no difference was found in terms of quality of sleep between the study arms during the 7 days of evaluation.

*Delirium complications:* No difference was found in terms of delirium-related complications between the study arms [median: 0 (0-6) complications in acupuncture arm vs 0 (0-1) complications in SOC arm, p=0.665].

*Length of hospitalization:* The duration of hospitalization was similar in the 2 study arms [median: 13 (2-67) days in the acupuncture arm vs 12 (2-54) in the SOC arm, p=0.945].

*Functional status at discharge:* Katz ADL at discharge was similar in the two study arms [median: 2 (0-6) in the acupuncture arm vs 3.5 (0-6) in the SOC arm, p=0.945].

*Safety:* No safety event was reported according to daily AcupAE evaluation.

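### Adverse-event collection stops with the treatment week, so a patient needled to the end of that week is observed for only 0 to 2 days after the last session

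*Combined protocol and SAP*

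**What the plan says.** All places are in the combined protocol and SAP.

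- **Collection window** (METHODS, Outcomes): "All daily outcomes were collected daily for one week after randomization or until the patient was discharged from the hospital".
- **Last day** (Secondary outcomes, item 1): the CAM-S sum runs "from day 2 (before treatment in the second day of the study) until day 7 (last day of evaluation"). The first study day is therefore day 1 and collection ends on day 7.
- **Adverse events** (Secondary outcomes, item 8): "All adverse events were recorded and monitored daily". The item has no end date of its own and describes no contact after treatment. The severe events that require exclusion from the trial are "pneumothorax, massive bleeding, or infection in the acupoint area requiring systemic antibiotic treatment".
- **Needling window** (Interventions): "up to 5 sessions of acupuncture in a 1-week period or until discharge". Treatment regimen repeats this as "up to five treatments in the one-week study period (treatments was not provided on weekends") and adds that sessions end once the patient has been free of delirium for 48 hours.
- **Result** (Secondary endpoints, Safety): "No safety event was reported according to daily AcupAE evaluation".

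**The concern.** The treatment period and the safety period are the same seven days, and both close early at discharge. Nothing in the plan provides for observation after the last needle. For a patient treated until the window closes, the checklist can end on the day of the last session.

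This affects an event that needs time to become visible. An infection at a needle site that goes on to need systemic antibiotics is the clearest case among the three named events. The patients concerned are those whose delirium persists, because they go on being eligible for sessions. Exposure can thus be greatest where observation after exposure is shortest. What is at stake is how much the zero-event safety result can support; the efficacy results are not touched.

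**Working it through.** The documents give no figure for observation time after the last session, so there is none to reproduce. It can be counted from the calendar.

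**Inputs**

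- Study days 1 to 7, with day 7 the last (Secondary outcomes, item 1).
- At most five sessions, none on weekends (Treatment regimen). A Friday-Saturday weekend is assumed; it is inferred from the allocation days.
- Diagnosis on Sunday, Monday, Wednesday or Thursday leads to acupuncture (Randomization).

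**Formula:** days observed after the last session = 7 − (study day of the last permitted session).

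Any seven consecutive days contain exactly five non-weekend days, so the cap of five sessions never ends needling early.

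| Start day | Permitted session days, Sunday to Thursday | Days left | Permitted session days, four allocation days only | Days left |
|---|---|---|---|---|
| Sunday | 1, 2, 3, 4, 5 | 7 − 5 = 2 | 1, 2, 4, 5 | 7 − 5 = 2 |
| Monday | 1, 2, 3, 4, 7 | 7 − 7 = 0 | 1, 3, 4, 7 | 7 − 7 = 0 |
| Wednesday | 1, 2, 5, 6, 7 | 7 − 7 = 0 | 1, 2, 5, 6 | 7 − 6 = 1 |
| Thursday | 1, 4, 5, 6, 7 | 7 − 7 = 0 | 1, 4, 5, 7 | 7 − 7 = 0 |

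**Sensitivity**

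- *Start day.* Randomization may follow diagnosis by up to 48 hours. Starts on Tuesday, Friday or Saturday leave 0, 0 and 1 days, still within 0 to 2.
- *Day numbering.* If the first day is day 0, each figure rises by one, giving 1 to 3 days.
- *Discharge.* A session on the day of discharge leaves 0 days.
- *The 48-hour rule.* With first remission on day 2 and Sunday-to-Thursday sessions, the last session falls no later than day 3 or 4, depending on how the 48 hours are counted. This leaves 3 to 6 days across the four start days. With remission on day 6 the figures return to 2, 0, 0 and 0.

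**Room for later observation.** RESULTS, Baseline patient data, reports 14 of 50 acupuncture patients dead or discharged within the seven days. The remaining 50 − 14 = 36 (36/50 = 72%) were not, so some in-hospital time after day 7 exists for them. Its length is not reported.

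**The case against.** The strongest reply is that 0 to 2 days is a limiting case. The 48-hour rule stops early remitters sooner, and the acupuncture arm's median was 5.5 delirium-free days (Primary endpoint), so many patients probably had longer observation. The carry-forward rule for patients who died or were discharged may raise that median somewhat. No session counts are given, so nothing shows how many patients, if any, were needled on day 7. This stands, and it limits the point to patients treated late. That group need not be trivial: under Secondary endpoints, 19 of 11 + 6 + 9 + 19 = 45 acupuncture patients (42%) had a high-severity CAM-S sum. A severity sum is not a count of late sessions, however.

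Four stronger readings are tempting, and the documents do not support them.

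- *All three named events are delayed harms.* The protocol lists them as grounds for exclusion and does not call any of them delayed. The argument here is made only for acupoint infection, and its onset time is an assumption.
- *Most patients stayed well beyond day 7.* Length of stay was "median: 13 (2-67) days in the acupuncture arm vs 12 (2-54) in the SOC arm", but that is total hospitalization, whereas study days run from randomization. In the acupuncture arm 50 − 26 = 24 patients did not have prevalent delirium at admission (Table 1) and were enrolled during the stay, so part of their stay came before study day 1.
- *Every patient is seen at discharge.* Discharge ADL is an outcome, but patients who died have none, and no denominator is given.
- *The trial concluded that acupuncture is safe, or missed a harm.* Neither appears in the text. The safety sentence already ties itself to the daily checklist.

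It is also fair to say that sample size limits the safety result regardless of the window. With 0 events in 50 patients, the exact one-sided 95% upper limit is 1 − 0.05^(1/50) = 5.8%. That bound covers only events inside the window, so it does not answer the point.

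**Conclusion.** The point holds for acupuncture patients needled to the end of the permitted week. They have 0 to 2 days of adverse-event observation after the last session (1 to 3 under day-0 numbering), and none if the session falls on the day of discharge. For those sessions the collection rule could miss an acupoint infection needing systemic antibiotics.

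This rests on three assumptions: a Friday-Saturday weekend, an infection onset of at least 1 to 2 days, and the general Outcomes sentence governing adverse events because their own item has no end date. If later surveillance took place, one sentence saying so would settle the matter. The number of patients affected cannot be derived from the documents. No reported result is shown to be wrong; the zero-event statement supports less than its wording may suggest.

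**What to change.** Extend adverse-event capture from day 7 to hospital discharge:

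1. Repeat the adverse-event checklist at the existing discharge assessment, where Katz ADL is already evaluated.
2. Review the chart from day 8 to discharge for the three named severe events. Acupoint infection applies to the acupuncture arm only, since no SOC patient was needled.
3. For patients already treated, do this by chart review.
4. Until that is done, word the safety result as *no checklist event during the 7-day evaluation*, and report the days observed after each patient's last session.

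The cost is a sentence in the protocol and a little more data abstraction. The zero-event statement may become less favourable. No change to the treatment schedule is proposed.

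### Two primary measures are each tested at two-sided 0.05 with no success rule, so the single stated Type I error of 0.05 is not secured and the stated power covers only one of them

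*Combined protocol and SAP*

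**What the plan says.** All references are to the Combined protocol and SAP.

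- **Outcomes, primary outcome.** There is one endpoint, resolution of delirium within 7 days, "measured as time-to-first remission of delirium and number of delirium-free days". Neither measure is ranked above the other.
- **Sample size calculation.** The inputs are from one measure: "delirium-free days were $3.2 \pm 1.6$ in the acupuncture group as compared with $1.7 \pm 2.4$ in the control group". The error rates are given once: "Taking into account a Type I error (alpha) of 0.05, a power of 0.80, pairwise comparison between our two study arms". The result is that "we calculated a minimal sample size of 28 patients in each of the 2 study arms".
- **Statistical methods.** Time to remission is analysed by "Kaplan-Meier product limit survival estimator with log-rank between-group comparison and Cox regression was performed", the Cox model being there to adjust for potential confounders. Delirium-free days fall under the general rule of a t-test or a Mann-Whitney test, depending on distribution. "All comparisons were two-sided with" a "significance level set at" p<0.05.
- **Results, primary endpoint.** Both measures are tested and both have p<0.001. The adjusted Cox model has p=0.010. In describing that model, the text labels time-to-first remission as the primary outcome.

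No section gives a testing order, an alpha split, a requirement that both measures succeed, or a definition of a positive trial.

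**The concern.** A trial with two primary measures needs a rule that turns two p-values into one conclusion. Without it, the stated Type I error of 0.05 has no defined meaning for the primary claim. If a significant result on either measure would have been reported as success, there were two chances at 0.05. If both were needed, the error rate is safe, but the power statement describes a different and easier target.

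The text also pulls in two directions. The measure that was sized is delirium-free days; the measure the Results call primary is time-to-first remission. A reader cannot tell which of them the 0.05 and the 0.80 belong to.

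**Working it through.** **Step 1. Reproduce the stated sample size.** The inputs from the sample size calculation are a difference of 3.2 − 1.7 = 1.5 days, SDs of 1.6 and 2.4, alpha 0.05 (two-sided, from Statistical methods) and power 0.80. The normal approximation is n per arm = 2 × (1.960 + 0.842)² × SD² / 1.5².

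- Simple mean SD, (1.6 + 2.4)/2 = 2.0: 2 × 7.85 × 4.00 / 2.25 = 27.9, so 28 (29 by exact t).
- Root-mean-square SD, √[(1.6² + 2.4²)/2] = 2.04: 29.0, just above 29, so 30 (31 by exact t).
- SD pooled by pilot arm size (24 and 8), 1.82: 23.1, so 24 (25 by exact t).

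The document does not say which SD was used, but 28 is what a single test at 0.05 needs with SD 2.0. Nothing was set aside for a second measure.

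**Step 2. Error rate if either measure suffices.** For two independent tests it is 1 − 0.95² = 9.75%. For correlated tests it is the bivariate normal probability that at least one |Z| exceeds 1.96:

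| Correlation of the test statistics | At least one significant |
|---|---|
| 0 | 9.75% |
| 0.5 | 9.1% |
| 0.7 | 8.35% |
| 0.8 | 7.8% |
| 0.9 | 7.0% |
| 0.95 | 6.5% |
| 0.98 | 5.9% |
| 1 | 5.0% |

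The document gives no correlation. The two measures come from the same daily CAM ratings, so it should be high, but relapse after a first remission separates them.

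**Step 3. Simulate the correlation.** Daily delirium states were generated with no difference between arms. About 27% left early, as reported (14 + 8 = 22 of 81), and the last evaluation was carried forward as in Statistical methods. First remission was tested by log-rank and delirium-free days by Mann-Whitney. The daily remission and relapse chances are assumptions. Arm sizes were 28/28 (planned) and 50/31 (enrolled), with relapse chances of 0, 10%, 30% and 50% and 4,000 runs per setting.

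| Assumed daily remission | Correlation | Either significant | Both significant |
|---|---|---|---|
| 8% | 0.97–0.99 | 5.4–6.2% | 3.8–4.4% |
| 20% | 0.88–0.96 | 6.0–7.5% | 2.7–3.9% |
| 35% | 0.77–0.92 | 6.5–8.5% | 2.0–3.3% |

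Each test alone rejected in 4.4% to 5.8% of runs. The simulation standard error near 7% is √(0.07 × 0.93 / 4,000) = 0.4 percentage points, so the outer ends of the ranges are approximate. The Cox model is not included.

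**Step 4. Error rate and power if both are required.** The chance of a false joint claim cannot exceed that of either test alone, hence at most 5%. Power for the joint claim cannot exceed power for delirium-free days alone. With 28 per arm and SD 2.0 that is 0.80, so the stated power is an upper bound for this reading.

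**Step 5. Cost of splitting alpha equally.** At 0.025 per measure, (2.241 + 0.842)² = 9.51, and with SD 2.0 n = 2 × 9.51 × 4.00 / 2.25 = 33.8, so 34 per arm. With SD 2.04 it is 36. Exact t gives 36 to 37. Power for delirium-free days at 0.025 is 0.70–0.71 with 28 per arm and 0.84–0.85 with 50 and 31.

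**Step 6. Reported results.** Both p-values are below 0.001. They pass 0.05 in sequence, 0.025 each, Hochberg, and a both-required rule.

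**The case against.** The strongest reply is that the plan names one endpoint, measured by one thing *and* another, which can be read as requiring both. On that reading alpha is held without any correction. This is a fair reading and it limits the claim: the documents do not show that the error rate is above 0.05, only that it would be if either measure could carry the conclusion. The reply does not close the gap, because the rule is nowhere stated and the power was not calculated for a joint requirement.

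A reader might go further and infer that this design has a false-positive rate of 7% to 8%. The documents do not support that. Such a figure needs an either-suffices rule and a correlation of roughly 0.77 to 0.90, and neither is given. The Results report a median of 0 delirium-free days in the standard-of-care arm, which fits low daily remission better. In a separate null run at 6% to 12% daily remission, the either-significant rate was 5.4% to 7.2%. Any such figure is also nominal. Allocation followed the weekday of diagnosis and assessment was not blinded, so the trial's full false-positive risk is a different matter that this arithmetic does not measure.

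Two further replies stand. The Cox model is introduced as covariate adjustment of the time-to-remission comparison and reads as supportive already; it only needs the label. And a hierarchy written now, with the p-values known, cannot restore prespecified error control.

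**Conclusion.** The point holds as a gap in the decision rule. Two primary measures are each tested at two-sided 0.05, one Type I error of 0.05 is stated, only delirium-free days was sized, and the Results attach the primary label to the other measure.

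Its size depends on the missing rule. If either measure suffices, the nominal error rate is above 0.05 unless the tests are perfectly correlated: about 5.4% to 8.5% under the assumed daily rates, with 9.75% for independent tests. If both are required, it is at most 5%, and 0.80 is then only a ceiling on the planned power. All of this presumes valid allocation and unbiased assessment.

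It would be wrong to infer that multiplicity puts the reported finding in doubt. With both p-values below 0.001, no reasonable rule changes the conclusion. What needs repair is the stated alpha and the hierarchy. This should be corrected, but it is not critical.

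**What to change.** State one rule in Statistical methods and use the same primary label throughout. Either of these would do:

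- **Fixed sequence.** Test delirium-free days, the measure that was sized, at two-sided 0.05. Only if it is significant, test time-to-first remission at 0.05. The stated alpha and the sample size then refer to the same measure. The cost is that time-to-first remission becomes a key secondary result.
- **Hochberg.** Keep both. Claim both if the larger p-value is at most 0.05; otherwise claim the one with the smaller p-value if that is at most 0.025. In null simulations this held the error rate at 3.7% to 4.7%. The cost is a stricter threshold for one measure when the other fails.

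Stating that both measures are required would also hold alpha, but power would then have to be calculated for the joint claim.

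Under any rule, label the adjusted Cox model as supportive, and disclose that the hierarchy was set after the results were known. The change is a few sentences and needs no new data or analysis.

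### The trial is called randomized, but weekday of diagnosis fixed the arm, so allocation was foreseeable before enrolment and weekend diagnosis is strongly, though not completely, confounded with arm

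*Combined protocol and SAP*

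**What the plan says.** The Trial Design paragraph opens: "This is a pragmatic open-label randomized-controlled trial". Setting and participants speaks of patients being randomized within 48 hours. Outcomes dates follow-up from randomization ("All daily outcomes were collected daily for one week after randomization"), and the Results use the same word for the acupuncture arm.

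The Randomization section describes something else: convenience allocation following the acupuncturists' working days. There, "patients with delirium diagnosed on Sunday, Monday, Wednesday or Thursday were assigned to the acupuncture arm", and "patients with delirium diagnosed on Tuesday, Friday or Saturday were assigned to SOC arm". It adds that blinding was not feasible. No sequence, generator, concealment method or independent allocator is described.

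Three other statements bear on how the rule worked:

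- Under Setting and participants, investigators confirm delirium with the CAM and check all criteria "before the patient or his/her next-of-kin was approached for consent". The same paragraph says "Trial site investigators identified consecutive eligible patients admitted to internal medicine departments".
- The third inclusion criterion reads "Diagnosed with delirium or subsyndromal delirium within the past 48 hours".
- Under Treatment regimen, "treatments was not provided on weekends".

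**The concern.** A calendar rule is deterministic. Whoever knows the day of diagnosis knows the arm, and the investigators who confirm the diagnosis know the day. Two routes to bias stay open that concealed randomization would have closed.

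1. **Selection.** The decision to confirm a borderline case, approach a family or accept consent can depend, even unintentionally, on the known arm.
2. **Confounding by day.** Patients diagnosed at a weekend may differ from those diagnosed on weekdays, or be cared for or assessed differently, and weekend days feed only one arm.

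Table 1 and the Cox covariates deal with measured factors only, and day of diagnosis is not among the covariates. The primary endpoint paragraph nevertheless reads the adjusted hazard ratio of 0.267 (1/0.267 = 3.75) as a roughly fourfold increase in remission caused by acupuncture. Readers who rely on the label would assume that both routes were excluded by design.

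**Working it through.** **Label against rule.** Given the day, the arm is fully determined: four days give acupuncture and three give SOC. This contradicts the design label without any calculation. The stated sample size of 28 per arm is unaffected. It reproduces by the normal approximation from the pilot difference of 1.5 and the simple mean of the two SDs, 2.0.

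**Inputs.** From Results: 132 screened, 81 enrolled (50 acupuncture, 31 SOC), and a number needed to treat (NNT) of 3 for first remission. Two assumptions are needed:

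- The weekend is Friday-Saturday. The text does not define it, but no treatment was given at weekends, and this is the only adjacent pair of days outside the listed working days.
- The other five days have diagnosis rate 1 and each weekend day has rate r. The documents do not report r, so 0.5, 1 and 1.5 are used.

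**Weekend confounding.** All weekend diagnoses fall in SOC. Of the five weekdays, only Tuesday does.

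- Weekend share of SOC: w = 2r/(2r + 1)
- Expected Tuesday controls: 31/(2r + 1)
- Expected acupuncture share: 4/(5 + 2r), compared with the observed 50/81 = 61.7% by an exact binomial test
- With no true effect, risk difference = w × gap, where gap is the remission deficit in weekend-diagnosed patients. NNT 3 gives a risk difference of 1/3, so the required gap is (1/3)/w.

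| r | w | Tuesday controls | Expected acupuncture share | p for 50/81 | Required gap (points) | Effect of a 10-point gap (points) |
|---|---|---|---|---|---|---|
| 0.5 | 50% | 15.5 | 66.7% | 0.35 | 66.7 | 5.0 |
| 1 | 66.7% | 10.3 | 57.1% | 0.43 | 50.0 | 6.7 |
| 1.5 | 75% | 7.8 | 50.0% | 0.045 | 44.4 | 7.5 |

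If NNT 3 was rounded from anywhere between 2.5 and 3.5, the required gaps become 80.0-57.1, 60.0-42.9 and 53.3-38.1 points. The observed split is matched exactly when 5 + 2r = 4 × 81/50 = 6.48, so r = 0.74. Then w is about 60% and the required gap about 56 points.

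**Selection.** 132 − 81 = 51 screened patients (38.6%) were not enrolled. The text does not split them by weekday, and Figure 1 is not available here. All 51 may have been validly excluded. The 50:31 split is no evidence of manipulation.

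**Baseline balance.** With 50 and 31 patients, a standardised difference reaches p<0.05 only at about 1.96 × √(1/50 + 1/31) = 0.448. From the counts in Table 1, using the difference in proportions divided by √[(p₁(1−p₁) + p₂(1−p₂))/2]:

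- Normal mobilization, 24/50 vs 9/31: 0.40
- Normal cognition, 28/50 vs 12/31: 0.35
- Hearing or visual impairment, 26/50 vs 22/31: 0.40

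All three point towards a less impaired acupuncture arm. They may be chance, but non-significant tests do not show that the variables are equally distributed. Hearing or visual impairment is not in the Cox model.

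**The case against.** The allocation rule is openly disclosed, days included, so a careful reader of the Methods is not deceived. The Cox model is also introduced as an assessment of association. Both points are fair, but the disclosing sentence itself says patients were randomized, and the conclusion drawn from the model is causal.

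The documents describe no concealment, which is not the same as stating there was none, and consent details are deferred to a manuscript not available here. However, a calendar rule cannot be hidden from the investigators who confirm the diagnosis, so the description is fair. The 48-hour window does not itself make the arm foreseeable. The weekday rule and the order of diagnosis and consent do that; the window only allows time between diagnosis and enrolment.

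The weekend argument rests on an inferred weekend and an unreported r, and r = 1.5 fits the observed split poorly. The bias is sized on a crude risk difference, not on the adjusted hazard ratio. Consecutive screening limits selection. Prevalent delirium (52% in both arms), reason for admission (p=0.94) and baseline CAM-S (median 8 vs 9) are close. These points stand: the figures are illustrative, and they do not carry the conclusion. None of them makes a weekday rule random or covers unmeasured factors.

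**Conclusion.** The concern holds and must be fixed. The randomized label is wrong as written, and this rests on the documents' own text with no assumption needed. The arm was foreseeable before consent was sought.

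The weekend confounding is strong but not complete, because Tuesday supplies weekday controls. Its size depends on a Friday-Saturday weekend and on r. Over the range examined, 50-75% of SOC and none of the acupuncture arm would be weekend-diagnosed. A 10-point weekend deficit in remission would account for 5 to 7.5 of the roughly 33 points, so this route alone is unlikely to explain the whole result. Selection at consent cannot be quantified. The documents show the opportunity for bias, not that it occurred. The data support a quasi-randomized association, not the stated causal effect.

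**What to change.** **Required (wording only):**

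1. In Trial Design, Setting and participants, Randomization and Results, replace the randomization terms with *quasi-randomized, allocated by weekday of diagnosis, not concealed*, or with *allocation* where that reads better. In Outcomes, date follow-up as *one week after allocation*. In the primary endpoint paragraph, replace the fourfold causal sentence with *was associated with a higher rate of first remission*.

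**Supporting:**

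2. Add a sensitivity analysis of time to first remission and delirium-free days: Tuesday SOC versus all acupuncture patients, unadjusted, giving the estimate with 95% CI and no significance claim. State that it addresses weekend confounding only, leaves selection untouched (Tuesday was as foreseeable as Friday), and rests on perhaps 8 to 16 controls.
3. Tabulate enrolled patients by weekday of diagnosis, and screened, eligible and consented patients where the screening log allows.
4. Replace the claims of equal distribution and similarity at baseline with standardised differences.

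**Cost.** A weaker design label, one imprecise analysis and one table. The enrolled counts need only the date of diagnosis, which the rule itself required. For the precision of item 2, assume acupuncture remission p of 60-80% and SOC remission 33 points lower. The standard error of the unadjusted log hazard ratio is about √[1/(50p) + 1/(n(p − 1/3))]:

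- n = 31 (all controls): 0.31-0.39
- n = 16: 0.40-0.52, from about 4-7 control remissions
- n = 8: 0.54-0.71, from about 2-4 control remissions
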